#### 6.8.4 Physical Examination

Complete physical examination, including weight and assessments of the skin, head, eyes, ears, nose, throat, neck, thyroid, lungs, heart, abdomen (with palpation of the liver; and with measurement of abdominal girth for pediatric patients only), lymph nodes, extremities, and a general assessment (including edema). Height will be measured during screening only. Whenever possible, assessment of right upper quadrant pain will be performed.

#### 6.8.5 Graft-versus-Host Disease

Diagnosis of GvHD will be made through monitoring of the skin (i.e., rash), total bilirubin level (i.e., liver), stool output (i.e., gut), and by biopsy, as clinically indicated.

Acute GvHD (defined separately for patients  $\geq 45$  kg <45 kg) is defined using stages and grades according to Jacobssohn and Vogelsang ([Jacobssohn and Vogelsang 2007](#)), as shown in Table 8.

**Table 8 Staging and Grading of Acute Graft versus Host Disease**

	Skin	Liver Total bilirubin (mg/dL)	Gut Stool output (mL/day)
Stage			
0	No GvHD rash	<2	<500 or persistent nausea
1	Maculopapular rash <25% BSA	2-3	500-999 or 10-20 mL/kg/day for patients <45 kg
2	Maculopapular rash 25%-50% BSA	3.1-6	1000-1500 or >20-35 mL/kg/day for patients <45 kg
3	Maculopapular rash >50% BSA	6.1-15	>1500 or >35 mL/kg/day for patients <45 kg
4	Generalized erythroderma plus bullous formation	$\geq 15$	Severe abdominal pain with or without ileus
Grade			
I	Stage 1-2	None	None
II	Stage 3 or	Stage 1 or	Stage 1
III	—	Stage 2-3 or	Stage 2-4
IV	Stage 4 or	Stage 4	—

GvHD=graft-versus-host disease; BSA=body surface area.  
Source: Jacobssohn and Vogelsang 2007

Defibrotide (JZP-381)  
Clinical Trial Protocol: 15-007 Version 4.0

Jazz Pharmaceuticals, Inc.  
20 August 2018

---

Assessment for chronic GvHD will be performed using the Seattle Cancer Care scoring form (see [Appendix 5](#)). Assessment includes examination of rash, mouth, eyes, gastrointestinal tract, liver function tests, lungs, joints and fascia, genital tract, and other symptoms, as clinically indicated.

### 6.8.6 Neutrophil and Platelet Engraftment

Patients will be monitored for engraftment per the Schedules of Procedures and Assessment ([Appendix 1](#)), i.e., weekly during hospitalization up to Day +60 post-HSCT (including on Day +30 post-HSCT), and at the Day +100 post-HSCT and Day +180 post-HSCT, study completion, or early termination visits.

For patients who develop VOD and are administered rescue defibrotide, engraftment will be monitored weekly after administration of the first dose of defibrotide through resolution of VOD; at 30 days after the last dose of defibrotide; and at the Day +100 post-HSCT and Day +180 post-HSCT/ study completion/early termination visits ([Appendix 2](#)). The investigator will determine the dates for neutrophil engraftment and platelet engraftment based on the algorithm below. The dates for neutrophil and platelet engraftment will be recorded separately. The date of neutrophil engraftment is defined as the first date after HSCT of an absolute neutrophil count  $>0.5 \times 10^9/L$  that is maintained for 3 consecutive days. The definition of “absolute neutrophil count” includes both segmented neutrophils and “bands”, immature neutrophils. The date of platelet engraftment is defined as the first date after HSCT of a platelet count  $>20 \times 10^9/L$  without a platelet transfusion in the preceding 7 days.

### 6.8.7 Karnofsky/Lansky Performance Scores

Functional impairment will be assessed using the Karnofsky Performance Scale (PS) for patients  $\geq 16$  years of age and the Lansky PS for patients  $<16$  years ([Table 9](#)).

Defibrotide (JZP-381)  
Clinical Trial Protocol: 15-007 Version 4.0

Jazz Pharmaceuticals, Inc.  
20 August 2018

**Table 9 Karnofsky and Lansky Performance Scores**

Percentage	Karnofsky Scale (Patients ≥16 years of age)	Lansky Scale (Patients <16 years of age)
100%	Normal, no complaints, no evidence of disease	Fully active
90%	Able to carry on normal activity, minor signs or symptoms of disease	Minor restriction in physically strenuous play
80%	Normal activity with effort, some signs or symptoms of disease	Restricted in strenuous play, tires more easily, otherwise active
70%	Cares for self, unable to carry on normal activity or to do active work	Both greater restriction of and less time spent in active play
60%	Requires occasional assistance from others but able to care for most needs	Ambulatory up to 50% of time, limited active play with assistance/supervision
50%	Requires considerable assistance from others and frequent medical care	Considerable assistance required for any active play, fully able to engage in quiet play
40%	Disabled, requires special care and assistance	Able to initiate quiet activities
30%	Severely disabled, hospitalization indicated, death not imminent	Needs considerable assistance in quiet activities
20%	Very sick, hospitalization necessary, active support, treatment necessary	Limited to very passive activity initiated by others
10%	Moribund, fatal process progressing rapidly	Completely disabled, not even passive play

Source: [Karnofsky et al. 1948](#); [Lansky et al. 1987](#).

## 6.9 Removal of Patients from the Study or Study Drug

### 6.9.1 Handling of Early Terminations

All patients are free to withdraw from participation in this study at any time, for any reason, and without prejudice. The investigator must withdraw any patient from the study if the patient states that he/she wants to stop participating in the study. In addition, the investigator, the Sponsor, or its designee, may remove a patient from the study at any time and for any reason. Reasons for early termination from the study or study drug may include the following:

- Withdrawal of consent by patient or patient's parent/legal guardian or representative
- Adverse event which in the opinion of the investigator contraindicates continuation in the study
- Investigator considers it not in the patient's best interest to continue in the study
- Death
- Disease relapse
- Non-compliance with study drug
- Pregnancy
- Sponsor (or its designee) decision to terminate study

The specific reason for the discontinuation from study or study drug should be documented on the termination eCRF. If a patient or patient's parent/legal guardian or representative

Defibrotide (JZP-381)  
Clinical Trial Protocol: 15-007 Version 4.0

Jazz Pharmaceuticals, Inc.  
20 August 2018

---

withdraws informed consent, the specific reason for withdrawing the informed consent should be stated. It is vital to obtain follow-up data on any patient who discontinued study drug because of an AE.

Adverse events resulting in termination will be followed to the satisfactory resolution and determination of outcome as ascertained by the investigator (and/or the Sponsor or its designee). The data will be recorded on the appropriate eCRF.

### 6.9.2 Sponsor's Termination of Study

The Sponsor reserves the right to terminate the study at any time for clinical or administrative reasons, including but not limited to, the following:

- Low enrollment
- Concern for patient safety
- Termination based on recommendation of DMC at interim analysis

Upon notification by the Sponsor, such a termination must be implemented promptly by the investigator, if instructed to do so by the Sponsor, in a timeframe that is compatible with the patients' well-being.

### 6.10 Appropriateness of Measurements

The safety assessments used in this study are typical for a Phase 3 study and are based on the safety profile of defibrotide, as characterized in several clinical studies and post-marketing experience in another indication.

## 7 STUDY ACTIVITIES

A schedule of study procedures and assessments for patients in the DP and BSC arms is provided in [Appendix 1](#). A schedule of study procedures and assessments for patients who develop VOD during the study and are administered rescue defibrotide is provided in [Appendix 2](#).

Throughout the study, if a patient in either arm, and during either phase of the study (prophylaxis phase or VOD treatment phase), is at risk for exceeding maximal allowable blood draw limits (per Seattle Children's Hospital Guideline for Maximum Blood Volumes [in the opinion of the investigator], [Appendix 6](#)), the blood draw schedules may be adjusted or eliminated within the following guidelines to ensure patient safety. The investigator must document in medical records the rationale for eliminating any protocol-mandated blood tests:

- Investigators can eliminate or discontinue PK sampling and/or biomarker sampling as a first option.
- If elimination or discontinuation of sampling for PK (first) and biomarker (second) assessments still leaves a patient at risk of exceeding blood draw maximums as per [Appendix 6](#), investigators can opt for a less rigorous schedule of laboratory assessments (serum chemistry, hematology, and coagulation testing). Under these circumstances, the

sampling schedule for laboratory assessments, to be based on local institutional practice, must include all of the following (at a minimum), during all time periods when daily or twice weekly laboratory assessments are otherwise required:

- Sampling for bilirubin testing to be performed daily (up to Day +30 post HSCT if hospitalized)
- Sampling for serum chemistry and hematology testing to be performed at least 3 times weekly
- Sampling for coagulation testing to be performed at least once weekly

## 7.1 Pre-Treatment Period

### 7.1.1 Screening Period (Study Day -14 to -1)

The following procedures will be performed or information will be collected during the screening visit:

- Administration of informed consent/assent
- Review of inclusion/exclusion criteria
- Demographics
- Medical history
- Prior medications (i.e., current at the time of screening), all prior therapies for the underlying disease, and conditioning regimen
- Physical examination, including height, assessments of the skin, head, eyes, ears, nose, throat, neck, thyroid, lungs, heart, abdomen (with palpation of the liver; and with measurement of abdominal girth for pediatric patients only), lymph nodes, extremities, and a general assessment (including edema). Whenever possible, assessment of right upper quadrant pain will be performed.
- Weight
- Vital signs (blood pressure, pulse, respiratory rate, and body temperature)
- Serum/urine pregnancy test, for females of childbearing potential only
- Clinical laboratory tests (serum chemistry, hematology, and coagulation). NOTE: Clinical laboratory tests can be measured as part of the screening visit or within 14 days prior to the start of the screening window on a non-screening test if the test was performed as part of patient's routine standard of care. Therefore, if a patient's normal SOC labs include all labs required as screening labs for the protocol and are done within 28 days prior to baseline, these labs can be considered to serve as the patient's protocol-mandated screening labs, and elevated AST/ALT (> 2.5 times the upper ULN) or bilirubin (> 1.5 times the ULN) values therein can be considered as liver risk factors in the inclusion criteria for the study.
- Calculation of CrCl (using Cockcroft-Gault for adults and Schwartz formula for pediatric patients). If cystatin C is measured, GFR will be calculated using either the Grubb or Larsson formula.

Defibrotide (JZP-381)  
Clinical Trial Protocol: 15-007 Version 4.0

Jazz Pharmaceuticals, Inc.  
20 August 2018

---

- Abdominal ultrasound (to assess liver and ascites). If possible, the spot at which the mid-clavicular line intersects with the lower costal margin should be marked with a surgical marker pen. NOTE: Abdominal ultrasound during the screening visit can be completed after randomization (if required) but must be done prior to the baseline visit.

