### 5.4 Method of Assigning Patients to Treatment Arms

Patients will be randomly assigned to receive defibrotide prophylaxis or BSC in a 1:1 ratio in an open-label fashion after they qualify for participation in the study. The investigator or designee will access IWRS to obtain treatment assignments for patients eligible to participate in the study.

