**Table 4 Ascites Assessment**

Ascites Assessment by Ultrasound		Ascites Assessment for EPAC or Clinical Diagnosis of VOD a
Ascites at Baseline	Ascites Post-baseline	
Absent b	Absent	No
Absent	Present	Yes
Present c	Absent	Not Evaluable d
Present	Present	Not Evaluable
Not Evaluable e	Absent or Present or Not Evaluable	Not Evaluable
Absent or Present	Not Evaluable	Not Evaluable

a For diagnosis of VOD using the modified Seattle criteria.

b Ascites “absent” at baseline or any post-baseline ultrasound examination is defined as trace ascites or no ascites as determined by ultrasonography on the specified ultrasound examination.

c Ascites “present” at baseline or any post-baseline ultrasound examination is defined as the presence of any amount of free fluid greater than trace as determined by ultrasonography on the specified examination.

d Ascites “Not evaluable” in the context of ascites assessment for EPAC or clinical diagnosis VOD per modified Seattle criteria means that ascites cannot be used when determining whether or not VOD is present.

e Ascites “Not evaluable” at baseline or any post-baseline ultrasound examination means the measurement was not obtainable for any reason on the specified ultrasound examination

EPAC= Endpoint Adjudication Committee; VOD=veno-occlusive disease.

Note: Liver size and ascites must be confirmed by ultrasound as physical examination is insufficient to document these parameters. All imaging should be made available to the central imaging facility.

Defibrotide (JZP-381)  
Clinical Trial Protocol: 15-007 Version 4.0

Jazz Pharmaceuticals, Inc.  
20 August 2018

Note: Baseline values for weight and bilirubin level will be obtained within 24 hours before the first dose of conditioning regimen for the patients in the DP arm and on the day that conditioning begins for patients in the BSC arm. Baseline values for hepatic size and presence of ascites will be obtained during ultrasound examination at the screening visit.

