### 7.1.2 Randomization

Eligible patients will be randomly assigned to study treatment in IWRS on or before the baseline visit. Baseline/Study Day 1 is defined as day the before conditioning begins for patients randomized to the DP arm and the day that conditioning begins for patients randomized to the BSC arm.

For patients whose HSCT/conditioning is postponed after the patient has been screened and randomized but before starting in the study/study treatment:

- If the date of the next planned transplant is >30 days from last screening test, clinical laboratory tests (including for bilirubin values), and ultrasound need to be repeated, and patient eligibility for inclusion in the study needs to be re-assessed before the next planned date for HSCT. Please see additional guidance below:
  - If the patient is no longer eligible then the patient needs to be removed from the study via early termination and the reason for the early termination needs to be clearly documented.

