- c. Patients who develop clinical signs and symptoms of VOD after discharge from the hospital must be monitored twice weekly instead of weekly through Day +60 post-HSCT. If these patients are diagnosed with VOD per the modified Seattle criteria, they will begin treatment for VOD and follow the schedule of events in [Appendix 2](#).
- d. If the twice weekly visit falls within the window of the Day +30 post-HSCT visit, the Day +30 post-HSCT assessments should be performed at that visit.
- e. Eligibility must be confirmed before randomization.
- f. Randomization of patients should be the last screening activity performed.
- g. Prior medications include those current at the time of screening through baseline, all prior therapies for the malignant disease, conditioning regimen for HSCT, and GvHD prophylaxis. Review of planned conditioning regimen for GvHD prophylaxis to ensure that the eligibility criteria will continue to be met.
- h. Complete physical examination, including assessments of the skin, head, eyes, ears, nose, throat, neck, thyroid, lungs, heart, abdomen (with palpation of the liver and with measurement of abdominal girth for pediatric patients), lymph nodes, extremities, and a general assessment (including edema). Height will be measured during screening only. Whenever possible, assessment of right upper quadrant pain will be performed.
- i. Vital signs include blood pressure, pulse, respiratory rate, and body temperature. For the DP arm, intensive monitoring of vital signs will be recorded during the first and second infusion of defibrotide on the first day of defibrotide dosing (within 24 hours before the first dose of the conditioning regimen). For this intensive monitoring, vital signs will be recorded at pre-dose, and 15, 30, 60, and 120 minutes ( $\pm 5$  minutes) following start of infusion and at 15 minutes ( $\pm 5$  minutes) following the end of the first and second infusions.
- j. Clinical laboratory tests include serum chemistry (ALT, albumin, alkaline phosphatase, AST, BUN, calcium, chloride, creatinine, glucose, magnesium, phosphorus, potassium, sodium, total bilirubin [direct and indirect], total protein, CrCl [using the Cockcroft-Gault formula for adults and Schwartz formula for pediatric patients] and if cystatin C is measured, then GFR [using the Grubb or Larsson formula]); hematology (hemoglobin, hematocrit, MCV, WBC count with differential, platelet count); and coagulation (aPTT, INR).

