- k. Bilirubin must be assessed daily during hospitalization; other serum chemistry and hematology assessments may be performed a minimum of 3 times weekly and coagulation parameters may be assessed a minimum of once weekly at the discretion of the investigator (see [Section 7](#) for details) to ensure patient safety ([Appendix 6](#)). The investigator must document in medical records the rationale for eliminating any protocol-mandated blood tests.
- l. Bilirubin must be assessed twice weekly; other serum chemistry, hematology, and coagulation parameters may be assessed at the discretion of the investigator (see [Section 7](#) for details) to ensure patient safety ([Appendix 6](#)). The investigator must document in medical records the rationale for eliminating any protocol-mandated blood tests.
- m. These assessments are to be performed post-HSCT only.
- n. If a patient is discontinued early from the study, engraftment status can be reported at the Day+30 post-HSCT visit.
- o. Abdominal ultrasounds (see [Appendix 4](#)) will be performed to assess liver and ascites and may be performed more frequently than at the protocol-specified time points, as clinically indicated (e.g., if VOD is diagnosed). If possible, the spot at which the mid-clavicular line intersects with the lower costal margin should be marked with a surgical pen. The ultrasound during the screening visit can be completed after randomization (if required) but prior to baseline. The ultrasound at Day +180 post-HSCT is to be performed only if the patient's total bilirubin is  $>2.0$  mg/dL or the patient has signs/symptoms of VOD.
- p. Assessment of chronic GvHD includes examination of rash, mouth, eyes, gastrointestinal tract, liver function tests, lungs, joints and fascia, genital tract, and other symptoms, as clinically indicated.

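### The ultrasound that supplies baseline liver size and ascites may be done after open-label randomisation, which does not fit the schedule's own rule on the order of screening

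*Protocol*

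**What the plan says.** Two places in the protocol allow the screening ultrasound to follow randomisation. One is section 7.1.1: "Abdominal ultrasound during the screening visit can be completed after randomization (if required) but must be done prior to the baseline visit". The other is Appendix 1 footnote o: "The ultrasound during the screening visit can be completed after randomization (if required) but prior to baseline". Footnote f of the same appendix gives the opposite order: "Randomization of patients should be the last screening activity performed". Footnote e adds "Eligibility must be confirmed before randomization".

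Section 5.4 has patients assigned "in an open-label fashion after they qualify for participation in the study", and section 7.1.2 sets the latest time: "Eligible patients will be randomly assigned to study treatment in IWRS on or before the baseline visit". Section 7.1.2 also contains a second route to a late scan. If conditioning or transplant is postponed after randomisation, and the new transplant date is more than 30 days after the last screening test, the ultrasound is repeated.

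The scan's role is set out in section 6.3.1.1, in a note under Table 4: "Baseline values for hepatic size and presence of ascites will be obtained during ultrasound examination at the screening visit". Hepatomegaly is growth of more than 15%, and of at least 1 cm, over that baseline. Under Table 4, ascites counts towards VOD only if it was absent on the baseline scan. If it was present or not evaluable then, it cannot be used.

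The central imaging reader (6.3.1.2) and the EPAC (6.3.1.3) are blinded to treatment.

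**The concern.** A baseline taken before assignment cannot depend on the arm. A baseline taken after open-label assignment can, because the people who arrange and perform the scan may know the arm. Here the scan is the reference for two of the four parameters used to diagnose VOD. Protocol 11.8 describes the other two, weight gain and bilirubin, as the objective ones, so the exception falls on the two that depend more on the operator.

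A baseline liver recorded too long makes later hepatomegaly harder to meet, and one recorded too short makes it easier. A non-evaluable baseline scan removes ascites as a route to diagnosis. Blinded readers work from the images they receive, so they cannot undo a difference that arose when the images were acquired. The site's own diagnosis also matters. It gives access to rescue defibrotide through the IWRS (Protocol 3.1), and SAP 10.1 censors BSC patients at rescue when the EPAC does not confirm VOD.

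**Working it through.** **1. Order of events.** Footnote f puts randomisation last in screening. Section 7.1.1 and footnote o allow the ultrasound after it, provided that it precedes the baseline visit. Section 7.1.2 allows randomisation up to the baseline visit. All three limits can be met by scanning first and randomising afterwards, so the exception is not needed to keep the outer time limit. Eligibility does not depend on this scan: no criterion in 4.1 or 4.2 uses its liver length or ascites result. This explains why the exception was possible without breaking footnote e.

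**2. What is blinded.** Reading of images is blinded (6.3.1.2), and so is adjudication (6.3.1.3). Nothing in the documents blinds the local operator or the site. That leaves acquisition and the investigator's diagnosis.

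**3. Whether the analysis plan looks at it.** None of sensitivity analyses I to V in SAP 10.1.1 separates baseline scans done before randomisation from those done after it. SAP 11.8 provides only a listing of ultrasounds with their dates.

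**4. Design figure.** SAP 4.6 states 90% power for HR 0.46 with an average of 68 events.
- HR = ln(0.86)/ln(0.72) = 0.459.
- A two-look simulation with 360 completers, 28% against 14% events, an interim at 70%, boundaries 3.2905 and 1.9603, and futility at conditional power of 10% or less gives 89.7% power and 68.0 events on average.

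The stated figure reproduces. Changing the order of scan and randomisation does not alter it.

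**5. Effect of a baseline error on the hepatomegaly threshold (illustration).** The true liver lengths and the 0.5 cm error are assumptions. With true baseline length L and error e, the true growth needed is max[1.15(L+e), L+e+1]/L − 1.
- L = 13 cm, e = 0: 15.0%.
- L = 13 cm, e = +0.5: 1.15 × 13.5 = 15.525; 15.525/13 − 1 = 19.4%.
- L = 13 cm, e = −0.5: 1.15 × 12.5 = 14.375; 14.375/13 − 1 = 10.6%.
- L = 8 cm, e = +0.5: 1.15 × 8.5 = 9.775; 9.775/8 − 1 = 22.2%.
- L = 8 cm, e = −0.5: 1.15 × 7.5 = 8.625; 8.625/8 − 1 = 7.8%.

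**6. How sensitive the test is to misclassification that differs by arm (illustration).** Assume 180 patients per arm, a true event rate of 28% in both arms, and a net difference d in classified event rates, split equally between the arms (p₁ = 0.28 + d/2, p₂ = 0.28 − d/2). A two-proportion approximation to the one-sided rejection probability is Φ{[d − 1.9603·√(2 × 0.28 × 0.72/180)] / √[p₁(1−p₁)/180 + p₂(1−p₂)/180]}. The first square root is 0.0473, so the critical difference is 0.0928.
- d = 0: 2.5%.
- d = 1 point (0.9 patients in each arm): 4.0%.
- d = 2 points (1.8 patients in each arm): 6.2%.
- d = 3 points (2.7 patients in each arm): 9.2%.

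Such a shift could come only from patients scanned late. If their share is s, the net reclassification needed among them is (d/2)/s in each arm. The documents give neither s nor d.

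**The case against.** The case on the other side is substantial, and most of it stands.

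- **The rule.** Footnote f says should, and footnote o is a specific exception limited to cases where it is required. A reader might infer that the protocol breaches its own absolute rule. It does not. The passages are inconsistent and need to be reconciled.
- **The safeguard.** A reader might infer that blinded review is bypassed for these patients. The documents do not support that. Liver length and the ascites category used for adjudication come from blinded central reading, and the EPAC is blinded too. Acquisition is further standardised by an imaging protocol and, where possible, a skin mark. The Imaging Manual named in Appendix 4 is not among the documents, so how tightly it controls acquisition cannot be judged.
- **Ascites.** Losing ascites does not remove a criterion, because ascites is an alternative to weight gain of at least 5%. Biopsy alone can also establish VOD, and death is an event in its own right.
- **Other open-label exposure.** Every follow-up scan is acquired locally with the arm known. Baseline weight and bilirubin are taken on or after randomisation in all patients. Reordering one scan leaves this unchanged.
- **Timing by arm.** The latest permitted scan date differs between arms because the baseline visit is the day before conditioning in DP and the day of conditioning in BSC. The difference is one day and is trivial.

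What remains is narrower. Blinding the reading does not blind the acquisition, and follow-up scans cannot be taken before assignment, whereas this baseline can.

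**Conclusion.** The point holds in a limited form. The protocol allows an avoidable post-assignment baseline for two of the four VOD parameters and contradicts itself on the order. The exposure is confined to local image acquisition, including non-evaluable scans, and to the site's diagnosis with its consequences for rescue and censoring.

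Its size is unknown. The threshold figures show what any baseline error would do, whether before or after randomisation. They are not evidence of an error that differs by arm. The error-rate figures show only that the test is sensitive to a few misclassified patients, under assumed shifts. A reader might take them to mean that the primary result is biased, or biased towards defibrotide. The documents support neither, because they give no share of late scans, no size and no direction. The case for change rests on how easily the gap can be closed.

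**What to change.** - **Protocol.** Reconcile section 7.1.1 with Appendix 1 footnotes f and o so that the screening ultrasound is completed before the IWRS releases an assignment.
- **Reporting.** From scan and randomisation dates, report by arm how many patients had a baseline scan after randomisation. Flag repeat scans after postponement (7.1.2) separately, because reordering the first scan does not prevent them. Where such a patient also has a scan from before randomisation, use that one.
- **Analysis.** Add one sensitivity run of the primary test in SAP 10.1.1 that excludes patients whose only usable baseline scan followed randomisation. Late scanning and postponement can themselves follow assignment, so this run supports the ITT analysis and does not replace it.

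**Cost.** The scan is already mandatory before the baseline visit, and randomisation is allowed up to that visit, so the main change is one of order. The downside is that randomisation may have to wait for the scan. That matters where conditioning is close, since DP dosing starts before conditioning. Using an earlier scan for postponed patients means comparing their later images with it. Sample size, alpha and power are unchanged.
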